### **13.3.7.2. Laboratory Data**

Clinical laboratory values will be expressed using conventional units International System of Units (SI) units. The actual value and change from baseline (Day 1, prior to the first administration of study drug) to each on-study evaluation will be summarized for each clinical laboratory parameter, including hematology, clinical chemistry, coagulation and urinalysis. In the event of repeat values, the last non-missing value per study day/time will be used. In the event that Day 1 data are unavailable for a given patient/parameter, the Screening value will substitute as the baseline value.

Severity of select clinical lab measures will be determined using CTCAE v.4.03 criteria (e.g., those measures that have a corresponding CTCAE grade classification). Labs with CTCAE Grades  $\geq 3$  will be presented in a data listing. Shift tables that present changes from Baseline to worst on-study and Baseline to last on-study values relative to CTCAE classification ranges will be produced.

### **13.3.7.3. Vital Signs, Physical Examinations, and ECOG Performance Status**

The actual value and change from baseline (Day 1) to each on-study evaluation will be summarized for vital signs. Shift tables that present changes from baseline to worst on-study and last on-study ECOG performance status values will be produced. By-patient listings of all vital sign measurements and ECOG performance status scores will be presented in data listings.

Physical examination results at Screening, and physical examination results changes during the study, will be summarized. All physical examination findings will be presented in by-patient data listings.

#### **13.3.7.4. Electrocardiogram Results**

Electrocardiogram results will be summarized descriptively, including heart rate and PR, QRS, QT, and QTc intervals (calculated by the Fridericia correction formula) intervals. If Bazett correction is entered by the site, the Fridericia corrected QTc interval (QTcF) will be derived using the formula:  $QT/(RR^{1/3})$ , where  $RR = 60/\text{heart rate}$ . Actual values and changes from baseline will be reported for each study visit.

Electrocardiogram data for each patient will be provided in a data listing.

#### **13.3.7.5. Ophthalmic Examinations**

Ophthalmic examination findings will be summarized descriptively by visit. All ophthalmic examination findings will be presented in the data listings.

#### **13.3.7.6. Concomitant Medications**

The use of concomitant medications will be included in by-patient data listings.

#### **13.3.8. Procedures for Handling Missing Data**

The procedures for handling missing data will be performed per the SAP (version 1.0).

### **13.4. Changes in the Conduct of the Study or Planned Analysis**

All deviations from the original statistical analysis plan will be documented and provided in the final clinical study report.

## **14. REGULATORY, ETHICAL AND LEGAL OBLIGATIONS**

### **14.1. Regulatory and Ethical Compliance**

This clinical study was designed, and shall be implemented and reported in accordance with, the ICH Harmonized Tripartite Guidelines for Good Clinical Practice, with applicable local regulations (including European Directive 2001/20/EC and US Code of Federal Regulations Title 21), Division 5 of the Health Canada Food and Drug Regulations - Drugs For Clinical Trials Involving Human Subjects, and with the ethical principles laid down in the Declaration of Helsinki.

### **14.2. Institutional Review Boards/Ethics Committees**

The protocol and the proposed informed consent form (ICF) must be reviewed and approved by a properly constituted Institutional Review Board/Independent Ethics Committee/Research Ethics Board (IRB/IEC/REB) before study start. Prior to study start, the Investigator is required to sign a protocol signature page confirming his/her agreement to conduct the study in accordance with these documents and all of the instructions and

procedures found in this protocol and to give access to all relevant data and records to Karyopharm, Quality Assurance representatives, designated agents of Karyopharm, IRBs/IECs/REBs and regulatory authorities as required.

### **14.3. Regulatory Authority Approval**

Before implementing this study, the protocol must be approved by the relevant, competent regulatory authority.

### **14.4. Protocol Adherence**

Investigators ascertain they will apply due diligence to avoid protocol deviations. All significant protocol deviations will be recorded and reported in the CSR.

### **14.5. Amendments to the Protocol**

Any change or addition to the protocol can only be made in a written protocol amendment that must be provided by Karyopharm, and approved by Health Authorities where required, and the IRB/IEC/REB. Only amendments that are required for patient safety may be implemented prior to IRB/IEC/REB approval. Notwithstanding the need for approval of formal protocol amendments, the Investigator is expected to take any immediate action required for the safety of any patient included in this study, even if this action represents a deviation from the protocol. In such cases, Karyopharm should be notified of this action and the IRB/IEC/REB at the study site should be informed according to local regulations (e.g., the UK requires the notification of urgent safety measures within 3 days) but not later than 10 working days.

### **14.6. Informed Consent**

Eligible patients may only be included in the study after providing written consent (witnessed, where required by law or regulation) on an IRB/IEC/REB approved ICF.

Informed consent must be obtained before conducting any study-specific procedures (i.e., all of the procedures described in the protocol). The process of obtaining informed consent should be documented in the patient source documents. The date when a patient's informed consent was actually obtained will be captured in their eCRFs.

Karyopharm will provide to investigators, in a separate document, a proposed ICF that is considered appropriate for this study and complies with the ICH GCP guideline and regulatory requirements. Karyopharm or their designee must agree to any investigator suggested changes to this ICF before their submission to the IRB/IEC/REB, and a copy of the approved version must be provided to the Karyopharm or designee after IRB/IEC/REB approval. CCI

Each patient's informed consent document will reflect that samples collected may be used for pharmacogenomic investigations.

## **14.7. Patient Confidentiality and Disclosure**

The Investigator must ensure anonymity of the patients; patients must not be identified by names in any documents submitted to Karyopharm or their designees. Signed informed consent forms and patient enrollment log must be kept strictly confidential to enable patient identification at the site.

## **14.8. Collection, Auditing Study Documentation, and Data Storage**

### **14.8.1. Study Documentation, Record Keeping and Retention of Documents**

Each participating site will maintain appropriate medical and research records for this trial, in compliance with Section 4.9 of the ICH E6 GCP, and regulatory and institutional requirements for the protection of confidentiality of patients. Each site will permit authorized representatives of the sponsor and regulatory agencies to examine (and when required by applicable law, to copy) clinical records for the purposes of quality assurance reviews, audits and evaluation of the study safety and progress.

Source data are all information, original records of clinical findings, observations, or other activities in a clinical trial necessary for the reconstruction and evaluation of the trial. Examples of these original documents and data records include, but are not limited to, hospital records, clinical and office charts, laboratory notes, memoranda, evaluation checklists, pharmacy dispensing records, recorded data from automated instruments, copies or transcriptions certified after verification as being accurate and complete, microfiches, photographic negatives, microfilm or magnetic media, x-rays, and subject files and records kept at the pharmacy, at the laboratories, and medico-technical departments involved in the clinical trial.

Data collection is the responsibility of the clinical trial staff at the site under the supervision of the site Investigator. The study eCRF is the primary data collection instrument for the study. The Investigator should ensure the accuracy, completeness, and timeliness of the data reported in the eCRFs and all other required reports. Data reported on the eCRFs, which are derived from source documents, should be consistent with the source documents or the discrepancies should be explained. All data requested on the eCRF must be recorded. Any missing data must be explained. For electronic CRFs an audit trail will be maintained by the system.

The Investigator/institution should maintain the trial documents as specified in Essential Documents for the Conduct of a Clinical Trial (ICH E6 Section 8) and as required by applicable regulations and/or guidelines. The Investigator/institution should take measures to prevent accidental or premature destruction of these documents.

Essential documents (written and electronic) should be retained for a period of not less than fifteen (15) years from the completion of the Clinical Trial unless Sponsor provides written permission to dispose of them or, requires their retention for an additional period of time because of applicable laws, regulations and/or guidelines.

#### **14.8.2. Auditing Procedure**

In addition to the routine monitoring procedures, the Sponsor or the regulatory authority may conduct an audit or an inspection (during the study or after its completion) to evaluate compliance with the protocol and the principles of GCP.

The Investigator agrees that representatives of the Sponsor and Regulatory Authorities will have direct access, both during and after the course of this study, to audit and review all study-relevant medical records.

In the event that a major compliance or regulatory issues arises, the Sponsor may conduct an audit without prior warning.

#### **14.9. Disclosure of Information**

All information provided to the Investigator by Karyopharm, or their designee, will be kept strictly confidential. No disclosure shall be made except in accordance with a right of publication granted to the Investigator in the Clinical Trial Agreement.

No information about this study or its progress will be provided to anyone not involved in the study other than to Karyopharm, or its authorized representatives, or in confidence to the IRB, or similar committee, except if required by law.

#### **14.10. Discontinuation of the Study**

It is agreed that, for reasonable cause, either the Investigator or Karyopharm, may terminate the Investigator's participation in this study after submission of a written notice. Karyopharm may terminate the study at any time upon immediate notice for any reason including the Sponsor's belief that discontinuation of the study is necessary for the safety of patients.

#### **14.11. Reporting and Publication of Study Documentation**

Karyopharm assures that the key design elements of this protocol will be posted in a publicly accessible database such as [www.clinicaltrials.gov](http://www.clinicaltrials.gov). In addition, upon study completion and analysis of the resulting clinical data, the results of the study will be:

- Reported to appropriate, competent regulatory authorities in full compliance with International Conference on Harmonization (ICH) E3: Structure and Content of Clinical Study Reports. A primary clinical study report (CSR) may be written based on all available patient efficacy and safety data for the primary analysis; a final CSR may be submitted when all evaluable patients have completed the long-term follow up period, died, progressed, withdrawn consent, discontinued due to toxicity, or been lost to follow up. PK results may be reported in either CSR.
- Submitted for publication and/or posted in a publicly accessible database of clinical study results. Publication will be in a relevant peer-reviewed journal, with authorship status and ranking designated according to the acknowledged contributions of participating investigators, institutions and the Sponsor.

CCI

## APPENDIX 1. EASTERN COOPERATIVE ONCOLOGY GROUP (ECOG) PERFORMANCE STATUS CRITERIA

**Table 8: Eastern Cooperative Oncology Group (ECOG) Performance Status Criteria**

ECOG Performance Status Scale	
Grade	Descriptions
0	Normal activity. Fully active, able to carry on all pre-disease performance without restriction.
1	Symptoms, but ambulatory. Restricted in physically strenuous activity, but ambulatory and able to carry out work of a light or sedentary nature (e.g., light housework, office work).
2	In bed < 50% of the time. Ambulatory and capable of all self-care, but unable to carry out any work activities. Up and about more than 50% of waking hours.
3	In bed > 50% of the time. Capable of only limited self-care, confined to bed or chair more than 50% of waking hours.
4	100% bedridden. Completely disabled. Cannot carry on any self-care. Totally confined to bed or chair.
5	Dead.

Source: Oken MM, Creech RH, Tormey DC, et al. Toxicity and response criteria of the Eastern Cooperative Oncology Group. *Am J Clin Oncol.* 1982;5:649-655)

## APPENDIX 2. INTERNATIONAL STAGING SYSTEM FOR MULTIPLE MYELOMA

**Table 9: International Staging System for Multiple Myeloma**

Stage	Characteristics
Stage I	$\beta_2$ -microglobulin $<3.5$ mg/L, albumin $\geq 3.5$ g/dL
Stage II	$\beta_2$ -microglobulin $<3.5$ mg/L and albumin $<3.5$ g/dL, or $\beta_2$ -microglobulin 3.5-5.5 mg/L irrespective of the serum albumin
Stage III	$\beta_2$ -microglobulin $\geq 5.5$ mg/L

Source: Greipp PR, San Miguel J, Durie BG, et al. International staging system for multiple myeloma. *J Clin Oncol.* 2005;23:3412-3420

### APPENDIX 3. INTERNATIONAL MYELOMA WORKING GROUP RESPONSE CRITERIA, MYELOMA

**Table 10: International Myeloma Working Group Response Criteria (Kumar 2016)**

Standard IMWG Response Criteria 	
Response Subcategory	Response Criteria
Complete response (CR)	Negative immunofixation of serum and urine, disappearance of any soft tissue plasmacytomas (SPDs), and < 5% plasma cells in bone marrow aspirates
Stringent complete response (sCR)	CR as defined above plus normal FLC ratio  and absence of clonal cells in bone marrow biopsy by immunohistochemistry ( $\kappa/\lambda$ ratio $\leq 4:1$ or $\geq 1:2$ for $\kappa$ and $\lambda$ patients, respectively, after counting $\geq 100$ plasma cells  )
Very good partial response (VGPR)	Serum and urine M-protein detectable by immunofixation but not on electrophoresis or $\geq 90\%$ reduction in serum M-protein plus urine M-protein level < 100 mg per 24 hr
Partial response (PR)	$\geq 50\%$ reduction of serum M-protein plus reduction in 24-hr urinary M-protein by $\geq 90\%$ or to < 200 mg/24 hr. If the serum and urine M-protein are not measurable, a $\geq 50\%$ decrease in the difference between involved and uninvolved FLC levels is required in place of the M-protein criteria. If serum and urine M-protein and serum FLC assay are not measurable, $\geq 50\%$ reduction in plasma cells is required in place of M-protein, provided baseline bone marrow plasma cell percentage was $\geq 30\%$ . In addition to the above criteria, if present at baseline, a $\geq 50\%$ reduction in the size (SPD) of soft tissue plasmacytomas is also required. 
Minimal response (MR)	$\geq 25\%$ but < 49% reduction of serum M-protein and reduction in 24-hr urine M-protein by 50–89%. In addition to the above criteria, if present at baseline, a $\geq 50\%$ reduction in the size (SPD) of soft tissue plasmacytomas is also required. 
Stable disease (SD)	Not recommended for use as an indicator of response; stability of disease is best described by providing the TTP estimates. Not meeting criteria for CR, VGPR, PR, MR, or PD.
Progressive disease (PD) 	Any 1 or more of the following criteria: Increase of 25% from lowest confirmed response value in 1 or more of the following criteria: Serum M-protein with absolute increase of $\geq 0.5$ g/dL;

Standard IMWG Response Criteria	
Response Subcategory	Response Criteria
	
Serum M-protein increase <math>\geq 1</math> g/dL if the lowest M-component was <math>\geq 5</math> g/dL;
 
Urine M-protein (absolute increase must be <math>\geq 200</math> mg/24 hr);
 
In patients without measurable serum and urine M-protein levels: the difference between involved and uninvolved FLC levels (absolute increase must be <math>> 10</math> mg/dL);
 
In patients without measurable serum and urine M-protein levels and without measurable involved FLC levels: bone marrow plasma cell percentage irrespective of baseline status (absolute increase must be <math>\geq 10\%</math>);
 
Appearance of a new lesion(s), <math>\geq 50\%</math> increase from nadir in SPD of <math>> 1</math> lesion, or <math>\geq 50\%</math> increase in the longest diameter of a previous lesion <math>> 1</math> cm in short axis;
 
<math>\geq 50\%</math> increase in circulating plasma cells (minimum of 200 cells per <math>\mu</math>L) if this is the only measure of disease

Clinical relapse	
Clinical relapse requires 1 or more of the following criteria:
 
Direct indicators of increasing disease and/or end organ dysfunction (CRAB features) related to the underlying clonal plasma-cell proliferative disorder. It is not used in calculation of TTP or PFS but is listed as something that can be reported optionally or for use in clinical practice;
 
Development of new soft tissue plasmacytomas or bone lesions (osteoporotic fractures do not constitute progression);
 
Definite increase in the size of existing plasmacytomas or bone lesions. A definite increase is defined as a 50% (and <math>\geq 1</math> cm) increase as measured serially by the SPD of the measurable lesion;
 
Hypercalcaemia (<math>> 11</math> mg/dL);
 
Decrease in haemoglobin of <math>\geq 2</math> g/dL not related to therapy or other non-myeloma-related conditions;
 
Rise in serum creatinine by 2 mg/dL or more from the start of the therapy and attributable to myeloma;
 
Hyperviscosity related to serum paraprotein

Relapse from CR (to be used only if the endpoint is disease-free survival)	
Any 1 or more of the following criteria:
 
Reappearance of serum or urine M-protein immunofixation or electrophoresis;
 
Development of <math>\geq 5\%</math> plasma cells in the bone marrow;
 
Appearance of any other sign of progression (i.e., new plasmacytoma, lytic bone lesion, or hypercalcaemia see above)

Standard IMWG Response Criteria	
Response Subcategory	Response Criteria
Relapse from MRD negative (to be used only if the endpoint is disease-free survival)	Any 1 or more of the following criteria: Loss of MRD negative state (evidence of clonal plasma cell on NGF or NGS, or positive imaging study for recurrence of myeloma); Reappearance of serum or urine M-protein by immunofixation or electrophoresis; Development of $\geq 5\%$ clonal plasma cells in the bone marrow; Appearance of any other sign of progression (i.e., new plasmacytoma, lytic bone lesion, or hypercalcaemia)

Abbreviations: ASCT = autologous stem-cell transplantation; CR = complete response; CRAB features = calcium elevation, renal failure, anemia, lytic bone lesions; CT = computed tomography; DOR = duration of response; FDG = fluorodeoxyglucose; FLC = free light chain; hr = hour; Ig = immunoglobulin; IMWG = International Myeloma Working Group; MM = multiple myeloma; MR = minimal response; MRD = minimal residual disease; MRI = magnetic resonance imaging; NGF = next-generation flow; NGS = next-generation sequencing; PD = progressive disease; PET = positron emission tomography; PFS = progression-free survival; PR = partial response; sCR = stringent complete response; SD = stable disease; SPD = sum of the products of the maximal perpendicular diameters of measured lesions; TTP = time to progression; VGPR = very good partial response.

Source: [Kumar, 2016](#)

 All response categories require 2 consecutive assessments made any time before starting any new therapy; for MRD there is no need for 2 consecutive assessments, but information on MRD after each treatment stage is recommended (e.g., after induction, high-dose therapy/ASCT, consolidation, maintenance). MRD tests should be initiated only at the time of suspected CR. All categories of response and MRD require no known evidence of progressive or new bone lesions if radiographic studies were performed. However, radiographic studies are not required to satisfy these response requirements except for the requirement of FDG PET if imaging MRD-negative status is reported.

 Per IMWG, quantitative Ig levels by nephelometry may be used in place of SPEP for routine M-protein measurement for patients with IgA or IgD myeloma. Also, per IMWG, response may be confirmed if the patient fails to provide 24-hour urine sample collection after screening activities occur. See “Practical considerations for application of IMWG consensus criteria” section of the guidelines (page e340; Kumar, 2016).

 Derived from international uniform response criteria for MM ([Durie 2011](#)). MR definition and clarifications derived from Rajkumar ([Rajkumar 2011](#)). When the only method to measure disease is by serum FLC levels: CR can be defined as a normal FLC ratio of 0.26 to 1.65 in addition to the CR criteria listed previously. VGPR in such patients requires a  $\geq 90\%$  decrease in the difference between involved and uninvolved FLC levels. All response categories require 2 consecutive assessments made at any time before the institution of any new therapy; all categories also require no known evidence of progressive or new bone lesions or extramedullary plasmacytomas if radiographic studies were performed. Radiographic studies are not required to satisfy these response requirements. Bone marrow assessments do not need to be confirmed. Each category, except for SD, will be considered unconfirmed until the confirmatory test is performed. The date of the initial test is considered as the date of response for evaluation of time dependent outcomes such as DOR.

 All recommendations regarding clinical uses relating to serum FLC levels or FLC ratio are based on results obtained with the validated Freelite test (Binding Site, Birmingham, United Kingdom).

 Presence/absence of clonal cells on immunohistochemistry is based upon the  $\kappa/\lambda$  ratio. An abnormal  $\kappa/\lambda$  ratio by immunohistochemistry requires a minimum of 100 plasma cells for analysis. An abnormal ratio reflecting presence of an abnormal clone is  $\kappa/\lambda$  of  $> 4:1$  or  $< 1:2$ .

-  Plasmacytoma measurements should be taken from the CT portion of the PET/CT, or MRI scans, or dedicated CT scans where applicable. For patients with only skin involvement, skin lesions should be measured with a ruler. Measurement of tumor size will be determined by the SPD.
-  Positive immunofixation alone in a patient previously classified as achieving a CR will not be considered progression. For purposes of calculating time to progression and PFS, patients who have achieved a CR and are MRD-negative should be evaluated using criteria listed for PD. Criteria for relapse from a CR or relapse from MRD should be used only when calculating disease-free survival.
-  In the case where a value is felt to be a spurious result per Investigator discretion (e.g., a possible laboratory error), that value will not be considered when determining the lowest value.

Questions regarding interpretation of these criteria may be addressed by consulting the, “Practical considerations for application of IMWG consensus criteria,” section of the guidelines (page e340, [Kumar 2016](#)).

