4.1. PRIMARY EFFICACY ENDPOINT

4.1.1. Definition

The primary endpoint is ORR which is defined as the proportion of patients who achieve a confirmed PR or better (i.e., PR, VGPR, CR, or sCR), as assessed by the IRC, during or after the study treatment, before documented disease progression or initiating a new MM treatment.

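### In Table 10, VGPR is the only positive response category with no condition on baseline plasmacytomas, so a patient who cannot be a PR or MR because of them can still be a VGPR and an ORR responder

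*Protocol*

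**What the plan says.** SAP 4.1.1 defines the primary endpoint, ORR, as "the proportion of patients who achieve a confirmed PR or better (i.e., PR, VGPR, CR, or sCR), as assessed by the IRC". SAP section 4 has the IRC apply the IMWG criteria, which the protocol prints as Table 10 in Appendix 3. On soft-tissue plasmacytomas, that table says:

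- **CR:** they must have disappeared. sCR is defined as CR plus further conditions, so it inherits this.
- **PR and MR:** if plasmacytoma was present at baseline, a 50% or greater "reduction in the size (SPD) of soft tissue plasmacytomas is also required". Both rows carry this sentence.
- **VGPR:** nothing. The row offers two routes: M-protein visible on immunofixation but not on electrophoresis, or a 90% or greater "reduction in serum M-protein plus urine M-protein level < 100 mg per 24 hr". The VGPR wording in footnote 3 for disease measurable only by free light chains adds no plasmacytoma condition either.
- **SD:** the residual class, "Not meeting criteria for CR, VGPR, PR, MR, or PD".

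Two footnotes apply to every category. Footnote 1: "All categories of response and MRD require no known evidence of progressive or new bone lesions if radiographic studies were performed". Footnote 3: "all categories also require no known evidence of progressive or new bone lesions or extramedullary plasmacytomas if radiographic studies were performed".

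**The concern.** VGPR ranks above PR and MR and below CR, and all of those carry a plasmacytoma condition. Without one, the categories are not nested: a patient can be a VGPR without being able to meet PR. SAP 4.1.1 counts responders as PR or better, which presumes that each higher category implies PR.

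ORR is the only endpoint with a formal test (Protocol 13.1.1). On the printed wording the gap can only add responders. The same classification feeds the clinical benefit rate, the start date for duration of response, and the survival summaries by best response. It also leaves the IRC without a written rule in a case it may meet. Plasmacytomas found on examination are re-assessed on Day 1 of each cycle (Protocol Table 1, footnote 11), so an SPD value can be on file with no statement of whether it counts towards VGPR.

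**Working it through.** **1. Apply the rows literally.** Take a patient with baseline SPD 20 cm² and on-study SPD 18 cm². The change is (18 − 20)/20 = −10%. This falls short of the 50% reduction for PR and MR. It is not PD, which needs a new lesion or growth of at least 50%. Suppose there is no other evidence of progression and every reading is confirmed.

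| Serum M-protein | Urine M-protein | PR or MR? | VGPR? | Class | ORR responder? |
|---|---|---|---|---|---|
| −60% | below 200 mg/24 hr | No: SPD condition fails | No: fall below 90% | SD | No |
| −92% | 80 mg/24 hr | No: SPD condition fails | Yes: all printed criteria met | VGPR | Yes |

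The lesion is the same in both rows. The same step appears with 0% SPD reduction and urine M-protein at 50 mg/24 hr, down 60%: serum falls of 30%, 60% and 89% give SD, and 90% and 95% give VGPR. With a 50% SPD reduction the sequence is orderly: 30% gives MR, 60% and 89% give PR, 90% and 95% give VGPR.

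**2. Do the footnotes close the gap?** Footnote 1 concerns bone lesions. Footnote 3 mentions plasmacytomas, but as progressive or new ones, and only where imaging was done. A stable lesion is neither. Reading footnote 3 as barring any remaining plasmacytoma would contradict the PR row, which accepts a 50% reduction.

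**3. Size.** The documents give no plan figure to reproduce here. Inputs:

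- N = 122: Protocol synopsis, Study Numbers.
- VGPR in Part 1: 4/78 overall and 2/30 penta-refractory (Protocol Table 3).
- Share of VGPR patients with baseline plasmacytomas: 10-25% (assumption).
- Share of those shrinking by less than 50%: 50% (assumption).

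Expected VGPRs: 122 × 4/78 = 6.3, or 122 × 2/30 = 8.1.

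Expected affected patients = VGPRs × prevalence × non-shrinkage:

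- Low: 6.3 × 0.10 × 0.5 = 0.3, or 0.3/122 = 0.26 ORR points.
- High: 8.1 × 0.25 × 0.5 = 1.0, or 1.0/122 = 0.8 ORR points.

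**4. The decision rule.** SAP 4.1.2 declares success if the lower limit of the exact two-sided 95% interval exceeds 10%. The Clopper-Pearson lower limit for k of n is the 2.5% quantile of Beta(k, n − k + 1).

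- 20/122 = 16.4%, lower limit 10.3%: success.
- 19/122 = 15.6%, lower limit 9.6%: failure.

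One reclassified patient therefore matters only if the count is exactly 20. The binomial probability of that is about 6% at a true ORR of 20% (the Part 1 penta-refractory rate) and about 9% at 15%. At a true ORR of 20%, the chance of success is 86.8%. Lowering the responder rate by 0.26 to 0.83 points reduces it by about 1.5 to 5.5 points.

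**The case against.** Table 10 is attributed to a published consensus standard, and the protocol and SAP bind the IRC to it. That source is not available here, so nobody can tell from these documents whether the VGPR row is a faithful copy or has lost a clause. Appendix 3 sends questions of interpretation to the source, and Protocol 7.3 leaves IRC procedures to the IRC Charter. Either may already hold a rule. An IRC could also read PR or better as meaning that a VGPR is a PR with a deeper M-protein fall.

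This stands as far as it goes. It makes checking the source the first step, and it rules out saying that such patients will certainly be counted. It does not close the gap: no passage in the protocol or SAP says that a VGPR must also meet PR, and the printed row says otherwise. Even if the row is faithful, this trial's tested endpoint still needs a stated rule.

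A reader might infer that the PR, MR and CR rows all exclude persistent extramedullary disease and that VGPR alone admits it. They do not. PR and MR accept up to half of the baseline SPD remaining; only CR and sCR require disappearance. The contrast is between less than 50% and at least 50% shrinkage.

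**Conclusion.** The point holds as an inconsistency in the printed response definition. VGPR alone among the positive categories has no plasmacytoma condition, and the literal rule admits responders who cannot meet PR. It is worth fixing because it touches the only tested endpoint and the fix is cheap.

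The size is small. The 0.3 to 1.0 patients is an expected count, not an upper bound, and it rests on assumed prevalence and non-shrinkage. In particular, nothing in the documents supports 50% non-shrinkage among patients whose M-protein has fallen by at least 90%.

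Three stronger inferences are not supported: that the plan dropped a clause from the standard (the source cannot be checked here); that at most one patient is affected (no document gives such a limit); and that the trial's result hangs on this (it does so only at the boundary, which is unlikely to be hit).

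**What to change.** Before the primary database snapshot (SAP 1.6):

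1. Check the VGPR row of Table 10 against the cited IMWG source and the IRC Charter.
2. State in Table 10 and SAP section 4 that a VGPR must also meet the PR plasmacytoma condition: at least 50% SPD reduction if present at baseline. A patient who meets the VGPR M-protein criteria but not this condition is SD if not PD.
3. Apply the same rule to Part 1 patients wherever they are pooled with Part 2, as in the All Penta-ref population (SAP 3.1.3).
4. If the cited standard has no such clause, record the rule as a trial-specific convention and report ORR with and without it.

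The cost is one line in each document, a note to the IRC, a re-check of any VGPR patient with baseline plasmacytomas, and possibly one extra ORR row. The change can only lower ORR or leave it as it is. It needs no new assessment for lesions followed on examination. Lesions seen only on imaging are re-assessed at the investigator's discretion (Table 1, footnote 10), so the IRC note should say how a missing SPD is handled. The change affects classification only, not patient care.
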